#### 6.2.6.2 *Feasibility of patient-led self-administration of study drug, including:*

Feasibility is measured by:

- Percent of subjects who consent to the study
- Percent of subjects who withdraw from the study
- Percent of subjects who are certified for self-administration of study drug
- Percent of subjects who return to clinic with a recurrent episode of PAF within 8 months of signing consent, and the associated timeframe(s) to time(s) of recurrence
- Percent of subjects that independently set up and inhale study drug according to the provided instructions

Endpoint will be reported, refer to SAP section 9.2.5. for the analysis of the endpoint

#### 6.2.6.3 *Proportion of subjects whose AF converted to SR*

Endpoint will be reported, refer to SAP section 9.2.5. for the analysis of the endpoint

#### 6.2.6.4 *Hand Held Echo (HHE) endpoints*

Protocol includes HHE endpoints for Part C:

- Proportion of subjects for whom capture and assessment of a diagnostic echocardiogram using a HHE at screening was successful
- Percent of subjects who are considered ineligible for enrollment as a result of the HHE assessment
- Time from HHE administration to availability of HHE report/results

The HHE sub-study was not included in Part C PLS; hence the above endpoints will not be reported for this part of the trial.

---

## FLE-002 (INSTANT) – Final Analysis

## Statistical Analysis Plan

---

### 7 General Statistical Considerations

#### 7.1 Sample Size and Power

Part C MLS and PLS did not have an enrollment target; enrollment was planned to continue in the Part C MLS at the discretion of the Sponsor to support rollover participation in the Part C PLS. December 31, 2021 Sponsor decided to stop enrollment in Part C MLS.

No formal hypothesis testing is planned for Part C. Summary statistics will be generated, including estimate of the endpoints and for the primary efficacy endpoint (refer to SAP section 9.2.1) its 90% confidence interval.

##### 7.1.1 Treatment Allocation

All subjects in the Part C MLS and in the Part C PLS study who are enrolled are assigned to a 120 mg eTLD (2 x 60 mg) FlecIH-103 dose regimen.

The site is permitted to enroll a subject before the monitoring period is finished. Thus, between time of enrollment and the end of the screening period, a subject can cease to be considered eligible if there is a change in the subject's status with regard to the study Inclusion or Exclusion criteria. In this case, the subject will not start study drug. These subjects are not reported as screen failures.

Subjects who are screened but did not start study drug (regardless of if the subject was enrolled or considered a screen failure) can re-enter the study when a new AF episode occurs. The statistical report will describe the reason(s) the subject did not start study drug when initially screened. Furthermore, the result of the secondary screening will be reported (e.g., if subject was enrolled and started study drug).

In the final report along with the Part C MLS subjects Part A and Part B subjects are reported who were assigned to a 120 mg eTLD (2 x 60 mg) FlecIH-103 dose regimen.

##### 7.1.2 Blinding and Unblinding

This is an open-label trial of a single study drug treatment. Thus, the processes of blinding and unblinding are not applicable in this study.

## FLE-002 (INSTANT) – Final Analysis

## Statistical Analysis Plan

### 7.2 Handling of Data

#### 7.2.1 Strata

Subjects are not stratified to any criterion.

#### 7.2.2 Examination of Patient Subgroups

For the HHE population (refer to section 8.6) results will only be reported for the specific HHE endpoints.

#### 7.2.3 Multiple Testing and Comparisons

There will be no multiplicity adjustments for the analyses outlined in this SAP.

#### 7.2.4 Visit Windows

After discharge two follow-up visits are planned, both are telephone assessments.

The first visit is planned on Day 2, 1 day after study drug administration.

Visit 2 is planned on Day 5, which is 4 days after study drug administration and coincides with End Of Study. Visit 2 may be completed within a  $\pm$  1 day window, meaning the visit can take place on Day 4, 5 or 6.

The statistical report will not take into account whether the visit occurred on the planned day or within the specified window; all visits will be reported, and visit dates will be included, along with the name of the corresponding visit (e.g., Visit 1, Visit 2) and its defined visit window.

If multiple assessments occur within a visit window, then the average of those assessments will be used for summarization and analysis.

For PLS subjects, Day 5 assessments of the Part C MLS study are not considered for the End of Study visit. Subjects who receive inhaled flecainide in the PLS part of the study are followed until Visit 2 (Day 5) of the PLS treatment. For PLS subjects who are enrolled for follow-up but do not receive inhaled flecainide, the End of Study form will show the reason why EOS was reached for the PLS.

#### 7.2.5 Imputation of Missing Data

##### Imputation of date and time values

Date and time values will only be imputed if the missing value impacts the reporting of Adverse Events, Conversion of AF to SR or recurrence of AF:

- For adverse events or recurrence of AF, the earliest possible date or time will be imputed.  
*Example: For AEs occurring after initiation of study medication for which the start time of the AE is missing, the time of initiation of study medication will be imputed to be the start time of the AE*
- In conversion from AF to SR, the last possible date or time will be imputed.  
*Example: If conversion to SR is known to have occurred between initiation of study medication and 60 minutes post initiation of study medication, but the time of conversion to SR is unknown: 60 minutes post initiation of study drug is imputed for time of conversion to SR.*
- For Treatment Emergent Adverse Events: a worst-case approach is used. If AE can be Treatment Emergent, event is assumed to be Treatment Emergent.  
For instance: if medication started at 12h:12m:45s and Adverse Event started at 12h:12m (seconds unknown) event is assumed to be Treatment Emergent

**FLE-002 (INSTANT) – Final Analysis****Statistical Analysis Plan****Conversion of AF to SR and recurrence of AF: frequency analysis.**

No missing information is expected: if Core Laboratory analysis is missing or incomplete, then investigator reported information is available (refer to section 6 SAP) for analysis. Should however information regarding the status of conversion to SR or recurrence of AF be incomplete, then the subject is assumed to be free of the event between time of last available information and the end of the reported period.

**Laboratory values below the limit of quantification**

If a laboratory reports a value below the limit of quantification (e.g., “<0.1” or “BLQ”) the value 0 will be imputed. Additionally, the value 0 will be imputed if the PK value for the sample taken just before initiation (at  $T_0$ ) is not available unless additional information indicates otherwise (refer to SAP section 9.2.2.10).

**Imputation of other missing values**

No imputation is planned for other missing values, nor is any sensitivity analysis planned. Missing values are assumed to be Missing Completely at Random (MCAR).

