6.4 B - Follow-up period

6.4.1 B – Telephone assessment (Visit 1): Day 2

The following procedures are completed during a pre-scheduled Day 2 telephone contact:

- Review of concomitant medications/treatments;
- Assessment of AEs;
- Assessment of AF-status (any recurrence);
- Assessment of the status of the subject's AF symptoms;
- Reminder to the subject to collect a remote ECG recording.

INSTANT Study Clinical Study Protocol

Study no. FLE-002

Version 8.0 EU-1 Page: 61 of 117

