**FLE-002 (INSTANT) – Final Analysis****Statistical Analysis Plan**

-If Core Laboratory did not report Conversion of AF to SR, then the investigator reported information is used for the period for which no Core Laboratory information is available.

-If Core Laboratory reported Conversion of AF to SR, then the investigator reported information is not used. Subject already converted within the period analyzed by Core Laboratory.

These rules will be followed for *recurrence of AF*:

-If Core Laboratory did not report Recurrence of AF, then the investigator reported information is used for the period for which no Core Laboratory information is available.

-If Core Laboratory reported Recurrence of AF, then the investigator reported information is not used. This applies for recurrences during the Holter or TTM monitoring period. If AF recurrence occurs outside of the monitoring period but prior to Day 5, the event will be entered in the EDC as a recurrent AF episode by the investigator.

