### 9.2.2.3 *The proportion of subjects in SR on Day 2*

The Modified ITT Population will be used to determine the proportion of subjects in SR on Day 2. The rhythm status used for the evaluation of this secondary efficacy endpoint is derived from the remote ECG system, in which the subject's heart rhythm is recorded. A subject is considered in SR on Day 2 if the subject's sinus rhythm during the recording is longer in duration (in seconds) than any of the other reported rhythms (refer to SAS section 5.2). The variable is set to missing if no evaluable remote ECG recording is available for analysis.

The proportion is estimated by the number of subjects in SR on Day 2, divided by the total number of subjects with available data. The estimate for the proportion will be reported.

Analysis will be performed for:

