### **9.2.2.4 *The proportion of subjects with reduced or no AF symptoms at 30 minutes post dose***

The Modified ITT Population will be used to determine the proportion of subjects with reduced or no AF symptoms (compared to baseline) at 30 minutes post dose.

The evolution of symptoms (no symptoms, improved, unchanged or worsened) is a categorical variable, a subject is considered to have reduced or no AF symptoms at 30 minutes post initiation of dose (compared to baseline) if the symptoms are reported as either 'no symptoms' or 'improved'.

The proportion is estimated by the number of subjects meeting the endpoint divided by the total number of subjects with available data. The estimate for the proportion will be reported. The variable is set to missing if no information is available.

Analysis will be performed for:

- the complete Modified ITT population
- mITT subjects whose AF converted to SR by inhaled flecainide within 30 minutes post dose
- mITT subjects whose AF was not converted to SR by inhaled flecainide within 30 minutes post dose

Analysis will not be performed for the PLS population.

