**9.2.2.8 Proportion of subjects in SR on Day 5**

The Modified ITT Population will be used to determine the proportion of subjects in SR on Day 5 (second follow-up visit).

The rhythm status used for the evaluation of this secondary efficacy endpoint is derived from the remote ECG system, in which the subject's heart rhythm is recorded.

A subject is considered in SR on Day 5 if the subject's sinus rhythm during the recording is longer in duration (in seconds) than any of the other reported rhythms (refer to SAS section 5.2). The variable is set to missing if no evaluable remote ECG recording is available for analysis.

The proportion is estimated by the number of subjects in SR on Day 5, divided by the total number of subjects with available data.

The Modified ITT Population will be used to determine the proportion of subjects with reduced or no AF symptoms (compared to baseline) at discharge. Discharge is left to the discretion of the treating physician 90 minutes post dose (-10 minute window).

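### Day 2 and Day 5 sinus-rhythm proportions leave out subjects without an evaluable home ECG under an MCAR assumption, with no sensitivity analysis, although AF recurrence is asked about at the same telephone contacts

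*SAP*

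**What the plan says.** SAP 7.2.5 has specific rules for dates and times, for conversion and recurrence status, and for laboratory values below quantification. For everything else it states "No imputation is planned for other missing values, nor is any sensitivity analysis planned", and adds "Missing values are assumed to be Missing Completely at Random (MCAR").

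This rule governs the two rhythm-status endpoints. SAP 9.2.2.3 says of Day 2: "The variable is set to missing if no evaluable remote ECG recording is available for analysis". It then fixes the denominator: "The proportion is estimated by the number of subjects in SR on Day 2, divided by the total number of subjects with available data". SAP 9.2.2.8 does the same for Day 5: "The proportion is estimated by the number of subjects in SR on Day 5, divided by the total number of subjects with available data". Protocol 10.2.1.4 B and 10.2.1.9 B contain the same rule, so the SAP is not departing from the protocol.

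The recordings are made by the subject at home on Day 2 and Day 5 (Protocol 7.2 B). Both telephone contacts include "Assessment of AF-status (any recurrence"), in Protocol 6.4.1 B and 6.4.2 B. SAP 6 adds that when AF recurs outside the monitoring period but before Day 5, "the event will be entered in the EDC as a recurrent AF episode by the investigator".

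For the primary endpoint, SAP 9.2.1 counts unknown conversion status as no conversion and divides by all mITT subjects. SAP 6 fills missing core-laboratory Holter data with the investigator's report.

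**The concern.** An available-data proportion is unbiased only if having a recording is unrelated to rhythm. That is doubtful for an ECG the subject must make at home. Recurrent AF, further treatment, readmission or loss of contact could each affect both the rhythm and whether a recording is made. The SAP gives no reason for assuming otherwise. The sponsor had already treated this capture as something to be tested: remote capture of AF status at follow-up was a Part A feasibility measure (Protocol Synopsis, Part A endpoints).

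The clearest case is a subject who reports by telephone that AF has come back and has no evaluable recording. The trial then holds information pointing to not being in SR, yet the subject is removed from the denominator and not counted. With a single arm there is no control group in which a similar distortion might cancel. At stake is how far the reported Day 2 and Day 5 percentages can be relied on as a description of all treated mITT subjects.

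**Working it through.** The plan attaches no expected value, missing rate or precision target to these endpoints, so there is no planned figure to reproduce. The protocol's power calculation concerns the primary endpoint only and does not enter here.

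**1. The rules side by side**

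| Situation | Rule | Treatment |
|---|---|---|
| Conversion status unknown | SAP 9.2.1 | Counted as not converted, full mITT denominator |
| Holter analysis missing or partial | SAP 6 | Investigator report fills the gap |
| No evaluable ECG on Day 2 or Day 5, AF recurrence reported | SAP 9.2.2.3, 9.2.2.8 | Set to missing, out of the denominator |

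The substitution rules in SAP 6 are written for conversion and recurrence. The Day 2 and Day 5 sections do not invoke them.

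**2. Worst-to-best-case range**

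Let N be the number of mITT subjects, m the number without an evaluable recording, and x the number observed in SR.

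- Planned estimate: x/(N − m)
- Worst case (missing = not in SR): x/N
- Best case (missing = in SR): (x + m)/N
- Width: m/N, so each missing subject adds 1/N. That is 1/25 = 4.0 points, or 1/52 = 1.9 points.

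Inputs:

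- N = 25 is the planned Part B size (Protocol 10.3 B). Part B alone is not one of the cohorts in SAP Table 1.
- N = 52 is an assumed pooled size: 27 Part A FlecIH-103 subjects in the efficacy analysis (Protocol 1.4) plus 25 planned in Part B. The Part C medically-led number is not given and would add to this.
- The values of m and an observed SR rate near 70% are assumptions. The documents give neither.

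| N | m | Planned estimate | Worst case | Best case |
|---|---|---|---|---|
| 25 | 1 | 17/24 = 70.8% | 17/25 = 68.0% | 18/25 = 72.0% |
| 25 | 2 | 16/23 = 69.6% | 16/25 = 64.0% | 18/25 = 72.0% |
| 25 | 3 | 15/22 = 68.2% | 15/25 = 60.0% | 18/25 = 72.0% |
| 25 | 5 | 14/20 = 70.0% | 14/25 = 56.0% | 19/25 = 76.0% |
| 52 | 4 | 34/48 = 70.8% | 34/52 = 65.4% | 38/52 = 73.1% |
| 52 | 10 | 29/42 = 69.0% | 29/52 = 55.8% | 39/52 = 75.0% |

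**3. Direction and size if data are not MCAR**

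Let p be the true SR rate, mS the missing rate among subjects in SR and mN the rate among those not in SR. The available-data proportion then estimates

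p(1 − mS) / [p(1 − mS) + (1 − p)(1 − mN)],

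which equals p only when mS = mN. With p = 70%:

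- mS = 5%, mN = 20%: 0.665/(0.665 + 0.240) = 73.5%, or +3.5 points
- mS = 5%, mN = 30%: 0.665/(0.665 + 0.210) = 76.0%, or +6.0 points
- mS = 20%, mN = 5%: 0.560/(0.560 + 0.285) = 66.3%, or −3.7 points

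For p between 60% and 80%, the three patterns give +2.6 to +4.0, +4.4 to +7.1, and −2.9 to −4.2 points. All of these missing rates are assumed.

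**The case against.** **Nothing formal rests on these proportions.** They are secondary and descriptive, and no testing is planned. They also include subjects cardioverted by other therapy after the 90-minute window, so they are not pure drug-effect estimates. This stands, and it limits the weight of the point.

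**A reader might infer that the plan leaves no way to bound the effect.** It does not. SAP 12 requires tables to show the population size, the number contributing and any missing observations. The bounds can be worked out from those counts, and results are also split by whether inhaled flecainide converted the subject. What is missing is a planned presentation of the bounds, and any use of the reported recurrences.

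**A reader might infer that the percentages are biased upward.** The documents do not establish this. A well subject may also skip a recording, and the third pattern in the working shows a downward bias. The distance to the worst case is not an estimate of bias.

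**A reader might extend the point to the symptom endpoints**, which share the denominator rule: "The proportion is estimated by the number of subjects meeting the endpoint divided by the total number of subjects with available data". The argument does not reach them. Those questions are asked in clinic at 30, 60 and 90 minutes on Day 1 (Protocol 7.3 B), and discharge is not allowed before 80 minutes post dose (Protocol 6 B). There is no home recording to miss, and the telephone contacts come on later days.

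**Telephone status is an imperfect substitute.** It asks about any recurrence, not rhythm at the time of the call, and is not ECG-confirmed. Its meaning is unclear for a subject who never converted. The recording may be made during the same call, so the two may be missing together. All of this stands, and it is why such a row can only be supportive.

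**SAP 11 allows unplanned analyses if they are identified as such.** True, but rows fixed in advance are more convincing than rows chosen after the missing pattern is known.

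**Conclusion.** The point holds for Day 2 and Day 5 SR. The SAP rests both proportions on an unsupported MCAR assumption for self-made home recordings, and plans no check. It makes no use of AF recurrence reported by telephone or entered in the EDC when the ECG is missing. It is also more lenient than the SAP's own primary-endpoint rule.

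The actual effect cannot be stated, because the documents give neither a missing rate nor a Day 2 or Day 5 SR rate. What follows from arithmetic alone is the width of the range: 4 points per missing subject at N = 25 and about 2 at an assumed pooled N of 52. The size of the Part C medically-led cohort is not given, so its width cannot be computed. The primary endpoint is untouched. This is a cheap improvement to two descriptive endpoints and does not call the trial's main result into question.

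**What to change.** Keep the available-data proportion as planned. For Day 2 and Day 5, in each reported cohort, add:

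- **Worst-case and best-case rows over all mITT subjects:** missing counted as not in SR, and missing counted as in SR.
- **A supportive row** in which a subject with a missing ECG and a telephone- or EDC-reported AF recurrence not known to have resolved counts as not in SR. Footnote that this status is not ECG-confirmed and records any recurrence, not the rhythm at the time of the call.

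Amend the sentence in SAP 7.2.5 that rules out sensitivity analysis so that it allows these rows. No new data are needed. The cost is a few table rows per endpoint and a less favourable lower bound on display.

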## 8 Study Populations

The final analysis for the INSTANT study will primarily focus on data for the MLS populations (Part A, part B and Part C) receiving 2x60mg FleIH-103 formulation using the prespecified definitions described in Section 8.1 through 8.6. Data for each MLS population will be presented for several cohorts, as described below and further defined in Section 8.7.

Due to the low number of subjects who participated in the PLS, a more limited analysis will be conducted on the PLS populations described in Section 8.8. Data for the PLS will only be presented for the overall study populations as defined in Section 8.8, with no additional cohort analyses.

Cohorts of the MLS populations include the Part C MLS Cohort (Section 8.7.1) and a Pooled MLS Cohort (Section 8.7.2); the latter of which consists of all MLS subjects enrolled to receive 120 mg FleIH-103 in Part A, Part B and Part C of the study. The Pooled MLS Cohort will be further subdivided into two additional sub-cohorts: 1) patients in the Pooled MLS Cohort with no evidence of flecainide present in their predose PK sample (Pooled MLS No Predose Flecainide Cohort; Section 8.7.3), and 2) patients in the Pooled MLS Cohort with flecainide present in their predose PK sample (Pooled MLS Predose Flecainide Cohort; Section 8.7.4).

A consort diagram will present the number of subjects included in each MLS population (i.e., safety, mITT etc.), including the overall number of subjects in the study population and the number of patients in each cohort of that population.

Individual tables will summarize data for each MLS population as described below in the table. The numbers in the table denote the 4 cohorts that will be analyzed. Each Cohort is defined in the table footnote below. The specified Cohorts will be presented as columns within each table for the study population analyzed. For example, for adverse events, the table will be based on the Safety population with columns for each Cohort specified in the table below (i.e., Cohorts 1, 2, 3, and 4).

## FLE-002 (INSTANT) – Final Analysis

## Statistical Analysis Plan

Table 1: Analysis Populations by Characteristics

Data Type	MLS Populations		
	Safety 	PK 	miITT 
Demographics 	1,2,3,4	1,2,3,4	1,2,3,4
Efficacy	-	-	1,2,3,4
Safety	1,2,3,4	-	-
PK		2,3	
PD	1,2,3,4	2,3	

The numbers in the table denote each Cohort as follows (each are further defined in section 8.7):  
 1-Part C MLS Cohort;  
 2-Pooled MLS Cohort;  
 3-Pooled MLS No Predose Flecainide Cohort;  
 4-Pooled MLS Predose Flecainide Cohort.

 Safety, PK and miITT populations are defined below in section 8 of the SAP

Including medical history, prior and concomitant medications, patient characteristics, etc.

### 8.1 Population of Consented Subjects

The population of consented subjects includes all subjects who signed the informed consent form (IC) for the MLS. Population includes Part A, Part B and Part C MLS subjects receiving 120 mg FleclH-103.

### 8.2 Intention-To-Treat Population (ITT)

The intention-to-treat (ITT) population includes all subjects that were enrolled (allocated). Compared to the Population of consented subjects, the ITT population excludes subjects who are not enrolled. Population includes Part A, Part B and Part C MLS subjects receiving 120 mg FleclH-103.

